#### Assigning Subjects to Treatment Groups

To minimise bias this study will employ both randomisation and blinding. Eligible, recruited participants will be assigned a participant number. The participant will receive the treatment that has been randomly allocated to that participant number.

Randomization codes will be kept in a sealed envelope in a secure filing cabinet. While the study is a double blind trial, study investigators will know the location of, and have access to, the sealed randomisation code envelope. This is in the event of an emergency where the content of the treatment is needed to be known. In the event that the code break envelope is opened, the ethics committee will be informed. Each participant's un-blinding would be considered on a case-by-case basis following authorisation by the Safety Committee which includes the study research nurses, the chief investigator ([name]) and advice from study members responsibly for medical oversight.

#### Prior and Concomitant Therapy

Participants will not be allowed to enter the trial if they are regularly taking the medications listed in 6.3 Exclusion Criteria. All participants will be informed at the beginning of the trial to maintain their normal medication regimen, if possibly (unless medically necessary), for the duration of the trial.

Participants who are irregular users of vitamin or mineral supplements will be asked to maintain their regular habits during the trial. Those taking flavonoids containing supplements (such as berry extracts or herbal supplements) will be asked to cease taking them 1 month prior to beginning the study and for the duration of the 12-week intervention. Participants will also be encouraged not to commence taking new over-the-counter supplements while partaking in the trial, unless instructed

to by their GP, and to inform the study team at any time if they change their medication for any reason.

Any changes to medication, including over-the-counter medications, will be documented in the participant's case report form.

Research Activity	Site	First Contact	Screening Visit	Baseline	During Intervention	After Intervention
Telephone Screening	Phone	X				
Participant Information Sheet	Post	X				
Informed Consent	CRF		Х			
Background Questionnaire	Post		Х			
QRisk3	Post		Х			Х
СВІ	Post		Х			Х
CCI	Post		Х			Х
GAD-7	Post		Х			Х
PHQ-9	Post		Х			Х
IPAQ	Post			Х		Х
PSQI	Post			Х		Х
Sunlight Exposure	Post			Х		Х
KSS	CRF			Х		Х
FFQ	Post			Х		
BPQ	Post			Х		Х
ACE-III	CRF		Х			Х
Digit Span	CRF			Х		Х
Interoception	CRF			Х		Х
RCFT	CRF			Х		Х
Sea Hero Quest	CRF			Х		Х
Supermarket Test	CRF			Х		Х
TMT	CRF			Х		Х
Actigraphy	Home			Х		Х
Adverse Events Reporting	CRF, NNUH		Х	Х	Х	Х
Blood Pressure	CRF		Х	Х		Х
Physical Measurements	CRF		Х	Х		Х
Blood Sample	CRF		Х	Х		Х
Urine Sample	Home		Х	Х		Х
Stool Sample	Home			Х		Х
Neuroimaging	NNUH			Х		Х

#### Table 1: Overview of research activities at each time point.

#### **Treatment Compliance**

Participant treatment compliance and any medical events or general comments about their experience taking the treatment will be monitored through regular phone contact with the investigators and recorded appropriately in the case report form.

Participants will be asked to return all remaining cranberry sachets at the end of the 12-week treatment period. The remaining sachets will also be an indicator of compliance.

Flavonoid metabolite concentrations will be quantified at baseline and following the 12-week intervention, and will be used to determine observance to the treatment.

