# Summary

Protocol Title	The impact of Cranberries On the Microbiome and Brain in healthy Ageing sTudy (COMBAT): a feasibility intervention			
Protocol Number	Version 4.0, 7 th May 2019			
Sponsor	The University of East Anglia, Norwich, United Kingdom			
Primary Contact	[name] [contact]			
Chief Investigator	[name] [contact]			
Study Personnel	[name] [contact]			
	[name] [contact]			
	[name] [name] [contact]			
	[name] [contact]			
	[name] [contact]			
	[name] [contact]			
	[name] [contact]			
	[name] [contact]			
	[name] [contact]			
	[name] [contact]			
	[name] [contact]			
	[name] [contact]			

	[name]
	[name] [contact]
	[name]
	[contact]
	[name]
	[name] [name]
	[contact]
Study Site/s	Bob Champion Research and Education Building
	Norwich Research Park
	[name]
	[name]
	United Kingdom
	Norwich Clinical Research Facility (CRF)
	Quadram Institute Building
	Norwich Research Park
	[name]
	[name]
	United Kingdom
	Quadram Institute Building
	Norwich Research Park
	[name]
	[name]
	United Kingdom
	Norfolk and Norwich University Hospital (NNUH)
	[name]
	[name]
	United Kingdom
	Norwich Biorepository
	Bob Champion Research and Education Building
	Norwich Research Park
	[name]
	[name]
	United Kingdom
	Imperial College London
	South Kensington
	[name]
	United Kingdom
	University of Parma
	[name]
	[name]
	Italy

Objectives	
 
i) Investigate the impact of cranberry intervention on gut microbiome composition and metabolism after a 12-week intervention.
 
ii) Investigate the role of microbiome modulation and metabolism in mediating the effect of the cranberry intervention on cognition and brain physiology (MRI)
 

Outcomes	
 
Gastrointestinal microbiota analysis
 
Cognitive function
 
Neuroimaging: MRI
 
Biochemical assessment: to include flavonoid metabolites
 

Design	Single-centre randomised, double-blind, placebo-controlled parallel intervention trial.
Participants	60 healthy adults (i.e. n=30 in treatment and control groups) aged 50 to 80 years.
Product to be Tested	Cranberry Institute freeze-dried cranberry powder estimated to contain 500mg plant-derived polyphenols per day.

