#### Urinary flavonoid analysis

For all participants, a minimum of two urine samples will be collected (baseline and follow-up) for purposes of assessing treatment adherence. All participants will be asked to provide the first morning void and to collect at least 100 mL of urine in a provided 200 mL container. Urine samples will be aliquoted in the laboratories and acid stabilisers added (i.e. Hydrochloric acid, ascorbic acid). Compliance will be monitored by quantifying 5 (total) key phenolic metabolites of flavanols and anthocyanins for comparison to levels in pooled baseline samples. Samples will be analysed by HPLC-MS using published methods (Czank et al., 2013).

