#### Analysis Populations

All participants selected for analyses must have completed the whole study. Any participants with data that inexplicably varies widely from the rest of their treatment group will be excluded from analyses.

In addition, any of the following will be considered a major protocol violation:

- Violation of inclusion or exclusion criteria that are deemed to affect efficacy.
- Non-compliance with assigned treatment regimen.
- Use of prohibited treatment or medication before or during the study, which is felt to affect the assessment of efficacy.
- Not receiving randomised treatment.

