# 11. Handling of Tissue

A suitably qualified member of the research team will obtain a 22ml venous blood sample at the initial screening visit and 32ml again at each of the baseline and follow-up visits. Someone competent in taking blood samples will undertake the collection of blood. Blood will be collected

and temporarily stored at CRF during clinic visits, then transported and stored long-term at the Norwich Research Park Biorepository.

If participants consent to having stool samples collected, these samples will be collected as close to the study as possible, within 48 hours. Participants will be provided with the necessary equipment including the sample jar, collection plate device, freezerbag, and gloves. Participants will be provided with an information form with clear instructions outlining how to collect and store the sample. Collection of these samples will be conducted by a member of the research team upon arrival at each study day. These samples will then be stored in short-term storage freezers at the CRF before transported and stored at the Norwich Biorepository.

If participants consent to having urine samples collected, they will be provided with the necessary equipment for collection including the sample jar and bag. These samples will be usually collected during the screening and follow-up research clinic visits. These samples will then be transported and stored long-term at the Norwich Biorepository.

The biological samples (including the DNA) collected during the intervention will be kept at the Norwich Biorepository for up to 10 years as the samples could be invaluable for future research in this area. Any subsequent analyses would be conducted in accordance and agreement with local ethical procedures. Volunteers will be asked if they agree to their anonymous samples being stored for future analysis as part of the consenting process.

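### Flavonoid metabolites, a listed outcome that can reveal missed product only in the cranberry arm, are allowed to contribute to the non-compliance violation

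*Protocol*

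**What the plan says.** Protocol section 7.2, Treatment Compliance, names three sources of information on adherence.

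- Compliance is "monitored through regular phone contact with the investigators".
- On returned product: "The remaining sachets will also be an indicator of compliance".
- On biochemistry: "Flavonoid metabolite concentrations will be quantified at baseline and following the 12-week intervention, and will be used to determine observance to the treatment".

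Section 8.5, Urinary flavonoid analysis, describes the urine check, which covers all participants: "Compliance will be monitored by quantifying 5 (total) key phenolic metabolites of flavanols and anthocyanins for comparison to levels in pooled baseline samples". Neither place gives an individual cut-off.

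Section 10, Analysis Populations, opens with rules on who is analysed (completers only, with extreme data removed). It then lists what counts as a major protocol violation, including "Non-compliance with assigned treatment regimen". It does not say what happens to violators.

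The Summary gives the fourth outcome as "Biochemical assessment: to include flavonoid metabolites". Section 7.2, Treatment to be Administered, puts the active dose at 500 mg total polyphenols per day. It matches the placebo on appearance, taste, energy and macronutrients, and states no polyphenol content for it.

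**The concern.** One variable measured after randomisation has two roles: it is an outcome, and it helps to decide who complied. As a measure of missed product it works in one arm only. A cranberry participant who skips sachets loses an expected rise in metabolites; a placebo participant who skips every sachet has none to lose.

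Nor does a low level mean only missed sachets. It also depends on absorption and on conversion by gut bacteria. Microbiome metabolism is the subject of objective i, and its mediating role is the subject of objective ii (section 4). A fully adherent person with a weak metabolic response can look non-compliant.

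If such people are left out, the cranberry arm loses its low metabolite responders while the placebo arm has no matching loss. The arms are then no longer comparable by randomisation. Any outcome correlated with the metabolite response, including the metabolite itself, can show a difference with no treatment effect behind it.

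**Working it through.** **1. The plan's own figure.** The protocol gives no number on this point. Its one computed result, 30 per group with a false discovery rate of 0.5% to 4%, does not bear on it. Only the group size of 30 and the 0.05 threshold are used below.

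**2. The chain in the text.**
- Metabolites help to determine compliance: stated (7.2 and 8.5).
- Non-compliance is a major violation: stated (10, Analysis Populations).
- Metabolites are an outcome: stated (Summary).
- A low metabolite level alone makes someone non-compliant: not stated.
- Violators are left out of the analysis: implied by the heading and the sentences before the list, but not stated.

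The follow-up level is measured after 12 weeks, too late to prompt withdrawal during treatment under section 6.5. The route to bias is therefore exclusion at analysis.

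**3. Size, if low-metabolite participants are excluded.** Let the metabolite response in the cranberry arm be normal and correlate r with an outcome scaled to SD 1, with no true effect. Removing the lowest fraction q shifts the cranberry mean by

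shift = r × φ(z_q) / (1 − q).

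- q = 0.10: 0.1755 / 0.90 = 0.195
- q = 0.20: 0.2800 / 0.80 = 0.350
- q = 0.30: 0.3477 / 0.70 = 0.497

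Multiplying by r gives the formula values below. Beside them are the results of a simulation of 20,000 trials, 30 per arm, two-sided t test at 0.05 (the protocol does not state sidedness). Both q and r are assumptions.

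| Removed from cranberry arm | r | Shift by formula (SD) | Shift simulated (SD) | Type I error |
|---|---|---|---|---|
| 10% (3 of 30) | 0.3 | 0.058 | 0.056 | 0.056 |
| 10% | 0.5 | 0.097 | 0.094 | 0.069 |
| 10% | 1.0 | 0.195 | 0.185 | 0.123 |
| 20% (6 of 30) | 0.3 | 0.105 | 0.103 | 0.064 |
| 20% | 0.5 | 0.175 | 0.167 | 0.091 |
| 20% | 1.0 | 0.350 | 0.336 | 0.277 |
| 30% (9 of 30) | 0.3 | 0.149 | 0.147 | 0.086 |
| 30% | 0.5 | 0.248 | 0.240 | 0.141 |
| 30% | 1.0 | 0.497 | 0.483 | 0.460 |

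The rows with r = 1.0 are the case where the metabolite is itself the outcome. At r = 0 the simulated shift is within 0.002 SD of zero and the type I error is 0.049 to 0.051.

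**4. Comparison.** Removing the same share from both arms, by a rule unrelated to outcome, gives shifts within 0.003 SD of zero and type I error of 0.048 to 0.053. An actual sachet rule need not be unrelated to outcome; this shows only what happens when the selection is neither one-sided nor outcome-dependent.

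**5. The urine sample.** Table 1, the sample table in section 8.5 and the urinary analysis text all include a baseline urine sample. Section 11 says instead that urine is "usually collected during the screening and follow-up research clinic visits". Section 11 is the outlier.

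**The case against.** The strongest reply is that the protocol never sets out the harmful sequence. It gives no metabolite cut-off, no link from the metabolite check to the analysis population, and no stated consequence for a violator. A protocol may leave the cut-off and the handling of violators to the analysis plan, which is not at hand, so their absence is no fault in itself. This stands, and it makes the concern conditional. It does not remove it, because the protocol itself fixes metabolites as a determinant of compliance and non-compliance as a major violation.

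A reader might infer that compliance rests on metabolites alone, so that no placebo participant could be found non-compliant. The text does not support that. Phone contact and returned sachets can flag either arm. A raised level in a placebo participant could also point to flavonoid supplements or restricted foods. What holds is narrower: a low metabolite level can reveal missed product only in the cranberry arm.

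It may also be said that a check applied to everyone against pooled baseline levels, read blind, would flag placebo participants simply for showing no rise, so it must be meant as monitoring. That is a fair reading. It also shows that the check can identify missed product in individuals only if allocation is known or guessed, which is a further reason to keep it out of decisions on who is analysed.

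Finally, the planned model is a repeated measures ANOVA, so the relevant correlation is with change from baseline, and stable personal traits would partly cancel. The protocol gives no figure for that correlation. At r = 0.3 with 10% to 20% removed, type I error rises only to 0.056 to 0.064.

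**Conclusion.** The point holds in conditional form. The protocol lets a listed outcome, informative about missed product in the cranberry arm only, contribute to a violation that sits in the section on who is analysed. If low levels lead to exclusion, that arm is selected on a post-randomisation outcome. As an illustration, removing the lowest 20% at a correlation of 0.3 to 0.5 shifts the arm mean by 0.105 to 0.175 SD. The shares and correlations are assumed, and the result also rests on normality and on no matching removal in the placebo arm.

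Two further inferences are not supported. One is that the bias must favour cranberry: it does so only where higher metabolites go with better results, it reverses where they go with worse ones, and it is zero with no correlation. The other is that the compliance reference is missing because section 11 omits baseline urine: three other places schedule that sample, section 11 says only what is usual, and metabolites are also measured in serum, with blood drawn at baseline and follow-up. That mismatch is a minor wording matter.

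The change is worth making because it closes a route to bias at almost no cost.

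**What to change.** - **Sections 7.2 (Treatment Compliance), 8.5 (Urinary flavonoid analysis) and 10 (Analysis Populations):** state that metabolite levels are used only as an outcome and to describe exposure by arm, never to include or exclude participants.
- **Basis of the violation:** define non-compliance by returned-sachet counts, supported by phone records, with one threshold for both arms set blind to allocation. The return instruction in section 7.2 names cranberry sachets; word it to cover both products.
- **Section 10, Analysis Populations:** make all randomised participants with data the main analysis, and confine exclusion for non-compliance to a secondary per-protocol analysis. This part is needed because a sachet rule is still selection after randomisation, and section 10 at present offers only a completer analysis.
- **Minor:** align section 11 with Table 1, the section 8.5 sample table and the urinary analysis text on the baseline urine sample.

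The cost is wording only, since sachet returns and phone contacts are already planned. The downside is that sachet counts can overstate intake; with the main analysis as above, this dilutes only the per-protocol analysis.

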#### Lifestyle Restrictions

In addition to the lifestyle exclusion criteria, for the duration of the 12m intervention and one month prior to baseline the participant will be asked to restrict the intake of particular foods as per Table 2 below.

#### Table 2: Food intake guidance

The following is a list of foods and beverages, which should be consumed less often during the study. Please try and check whether the foods to avoid are part of ready-made and packet meals. Other foods can be consumed without limitations.

Food	Guidance for Intake	Alternative Foods
Berries, red/black/purple	Please try to avoid during the	banana, orange, mango,
grapes or foods containing them	study	melon, , peach, pear, nectarine
Dark chocolate (e.g. >70%	Please try to avoid during the	milk chocolate, white
cocoa solids)	study	chocolate
Cocoa/dark chocolate drink	Please try to avoid during the	malted drink such as Horlicks
	study	
Tea (including herbal), medium	Try to limit to 4 or fewer mugs	malted drink such as
mug	per day	Horlicks, coffee, sugar-free
		soft drinks, water

On the day before the clinical visits at for screening, baseline and follow-up visits participants will be required to fast from 10pm the day before. For the 24 hours prior to clinical assessment participants are requested to refrain from exercising and alcohol and to consume their intervention food with breakfast on the day before the clinical visit.

7.3 Adverse Event Monitoring and Medication Changes

Procedures for recording and reporting adverse events are in place, with an adverse event (AE) being classified as any compromise of participant safety, and a serious adverse event (SAE) being defined as a compromise of participant safety that results in death; is life-threatening; requires hospitalisation or prolongation of existing hospitalisation; or results in persistent/significant disability/ incapacity. All AE's will be recorded and handled in accordance with Good Clinical Practice (GCP) guidelines. All AE's occurring after the subject has signed the informed consent must be fully recorded in the subject's case report form. Documentation must be supported by an entry in the subject's file. A laboratory test abnormality considered clinically relevant, e.g. causing the subject to withdraw from the study, requiring treatment or causing apparent clinical manifestations, or judged relevant by the investigator, should be reported as an adverse event. Each event should be described in detail along with start and stop dates, severity, relationship to investigational product, action taken and outcome.

ICH E6 defines an AE as any untoward medical occurrence in a patient or clinical investigation subject administered an investigational product regardless of its causal relationship to the study treatment. An AE can therefore be any unfavourable and unintended sign (including an abnormal laboratory finding), symptom, or disease temporally associated with the use of an investigational product.

At each assessment visit and phone contact, participants will be asked if they have experienced any AE's or (SAE's) since consenting to participate in the trial. Any adverse or serious adverse event data will be collected on the appropriate documentation. Trends in AE's and SAE's reporting will be monitored across all volunteers. Additionally, participants will be asked to report if they have started (or amended) any medications during the trial which will be noted on the case report forms.

If participants feel in anyway adversely affected by any treatment (including placebo), or the principal investigator feels an AE necessitates cessation, the participant would be advised not to continue and the appropriate measures will be taken (i.e. case report forms, contact research nurse and principal investigator if deemed necessary).

The occurrence of an AE may come to the attention of study personnel during study visits and interviews of a study subject presenting for medical care, or upon review of subject data by a study monitor. Any medical condition that is present at the time that the subject is screened will be considered as baseline and not reported as an AE. However, if it deteriorates at any time during the study, it will be recorded as an AE. All AEs must be graded for severity and relationship to study product.

Severity of Event: All AEs will be assessed by the clinician using a protocol defined grading system. For events not included in the protocol defined grading system, the following guidelines will be used to quantify intensity:

- **Mild**: events require minimal or no treatment and do not interfere with the subject's daily activities.
- **Moderate**: events result in a low level of inconvenience or concern with the therapeutic measures. Moderate events may cause some interference with functioning.
- **Severe**: events interrupt a subject's usual daily activity and may require systemic drug therapy or other treatment. Severe events are usually incapacitating.

Changes in the severity of an AE will be documented to allow an assessment of the duration of the event at each level of intensity to be performed. AEs characterized as intermittent require documentation of onset and duration of each episode.

**Relationship to Study Product**: The clinician's assessment of an AE's relationship to test article is part of the documentation process, but it is not a factor in determining what is or is not reported in the study. If there is any doubt as to whether a clinical observation is an AE, the event will be reported. All AEs must have their relationship to study product assessed by the PI using the following guidelines:

- **None**: The AE is definitely not associated with the study product administered.
- **Remote**: The study product is not likely to have had an association with the observed AE.
- **Possible**: The AE follows a reasonable temporal sequence from the study product, but could have been produced by the study subject's clinical state or other modes of therapy administered to the study subject.
- **Probable**: The AE follows a reasonable temporal sequence from study product administration, abates upon discontinuation of treatment, and cannot be reasonably explained by known characteristics of the study subject's clinical state.
- **Highly Probable**: The AE follows a reasonable temporal sequence from study product administration, abates upon discontinuation of treatment, and is confirmed by reappearance of the AE on repeat exposure (rechallenge).

Once a participant has reported experiencing an AE, participants will be followed up through regular telephone calls. Participants will be asked about their symptoms, and if medical advice has been sought.

All AEs including local and systemic reactions not meeting the criteria for "SAEs" will be captured on the appropriate case report form. Information to be collected includes event description, date and time of onset, clinician's assessment of severity, relationship to study product, and time of resolution/stabilization of the event. Additional information to be collected, if applicable, includes the treatment administered. All AEs occurring during the study must be documented appropriately regardless of relationship. All AEs will be followed until adequate resolution.

All adverse events occurring during the study will be reported and recorded whether or not they are considered to be non-serious, serious and/or related to the treatment. The following information will be required in each case:

- Subject and date
- Description of event
- Duration
- Frequency
- Intensity
- Seriousness
- Action taken
- Outcome and sequelae
- Relationship to test product

Documentation of all adverse events includes completion of the appropriate section of the case report form (AE).

Documentation of a serious adverse event requires that a separate form (SAE) be completed by the investigators in each case.

In addition, the ethics committee will be notified by the investigator of serious adverse events. Such events should be reported immediately by phone and followed by a faxed SAE form within 48 hours.

The risk of an AE or SAE arising from any of the research activities involved in the study is extremely low. Decisions regarding the causality of such events will be made at the relevant site by a medically qualified person associated with the study and will also involve the PI. In the case that an SAE is decided to be related to the study protocol, it will be recorded and reported using the non-CTIMP SAE reporting template provided by the HRA, and the final report will be completed and signed by the CI and sent to the relevant research ethics committee that issued the favourable opinion for the study.

